Appendix 1 OTL38 Dose Preparation Manual

[REDACTED]

[REDACTED]

[REDACTED]

[REDACTED]

[REDACTED]

[REDACTED]

[REDACTED]

[REDACTED]

[REDACTED]	[REDACTED]	[REDACTED]	[REDACTED]
[REDACTED]	[REDACTED]	[REDACTED]	[REDACTED]
[REDACTED]	[REDACTED]	[REDACTED]	[REDACTED]
[REDACTED]	[REDACTED]	[REDACTED]	[REDACTED]

[REDACTED]

[REDACTED]

[REDACTED]

[REDACTED]

[REDACTED]

[REDACTED]

[REDACTED]

[REDACTED]

[REDACTED]

[REDACTED]

[REDACTED]

[REDACTED]	
[REDACTED]	
[REDACTED]	
[REDACTED]	

[REDACTED]

[REDACTED]

[REDACTED]

[REDACTED]

[REDACTED]

[Redacted]

[Redacted]

[Redacted]

[Redacted]

[Redacted]

[Redacted]

[Redacted]

[Redacted]

[REDACTED]

[REDACTED]

[REDACTED]

[REDACTED]

[REDACTED]

[REDACTED]

[REDACTED]

[REDACTED]

[REDACTED]

[REDACTED]

[REDACTED]

[REDACTED]

[REDACTED]

[REDACTED]

[REDACTED]

[REDACTED]

[Redacted text block]

[Redacted text block]

[Redacted text block]

[Redacted text block]

[Redacted text block]

[Redacted]

[Redacted]

[Redacted]

[Redacted]

[Redacted]

[Redacted]

[Redacted]

[Redacted]

[Redacted]

[Redacted]

[Redacted]

[Redacted]

[Redacted]

[Redacted]

[Redacted]

[Redacted]

[Redacted]

[Redacted]

[Redacted]

- [Redacted]

- [Redacted]

- [Redacted]

- [Redacted]

[Redacted]

- [Redacted]

- [Redacted]

[Redacted]

[Redacted]

[Redacted]

[Redacted]

[Redacted]

[Redacted]

[Redacted]

[Redacted]

[Redacted]

[Redacted]

[Redacted]

[Redacted]

[Redacted]

[Redacted]

[Redacted]

[REDACTED]

[REDACTED]

[REDACTED]

[REDACTED]

Appendix 3 Detailed Description of the

[REDACTED]

[REDACTED]

[REDACTED]

[REDACTED]

[REDACTED]

[Redacted text block]

[Redacted text block]

[Redacted text block]

[REDACTED]

[REDACTED]

[REDACTED]

- [REDACTED]
- [REDACTED]
- [REDACTED]
- [REDACTED]

[REDACTED]

- [REDACTED]

[REDACTED]

[REDACTED]

[REDACTED]

[REDACTED]

[REDACTED]

[REDACTED]

[REDACTED]

[REDACTED]

[REDACTED]

[REDACTED]

[REDACTED]

[Redacted]

[Redacted]

[Redacted]

[Redacted]

[Redacted]

[Redacted]

[Redacted]

[Redacted]

[Redacted]	[Redacted]	[Redacted]
[Redacted]	[Redacted]	[Redacted]
[Redacted]	[Redacted]	[Redacted]
[Redacted]	[Redacted]	[Redacted]
[Redacted]	[Redacted]	[Redacted]

[Redacted]

[Redacted]	[Redacted]	[Redacted]
[Redacted]	[Redacted]	[Redacted]
[Redacted]	[Redacted]	[Redacted]
[Redacted]	[Redacted]	[Redacted]
[Redacted]	[Redacted]	[Redacted]

[Redacted]

[Redacted]	[Redacted]	[Redacted]
[Redacted]	[Redacted]	[Redacted]
[Redacted]	[Redacted]	[Redacted]
[Redacted]	[Redacted]	[Redacted]
[Redacted]	[Redacted]	[Redacted]

[REDACTED]

Appendix 4 Detailed Description of the

[REDACTED]

[REDACTED]

[REDACTED]

[REDACTED]

[REDACTED]

[REDACTED]

[REDACTED]

[REDACTED]

- [REDACTED]

- [REDACTED]

[REDACTED]

[REDACTED]

[REDACTED]

[REDACTED]

[REDACTED]

[REDACTED]

[REDACTED]

[REDACTED]

[REDACTED]

[REDACTED]

[REDACTED]

[REDACTED]

[REDACTED]

[REDACTED]

[REDACTED]

[REDACTED]

[REDACTED]

[REDACTED]

[REDACTED]

[REDACTED]

[REDACTED]

[REDACTED]

[REDACTED]

[REDACTED]

[REDACTED]

[REDACTED]

[REDACTED]

[REDACTED]

[REDACTED]

[Redacted]

[Redacted]

[Redacted]

[Redacted]

[Redacted]

[REDACTED]

[REDACTED]

[REDACTED]

[REDACTED]

[REDACTED]

[REDACTED]

[REDACTED]

[REDACTED]

[REDACTED]

[REDACTED]

[REDACTED]

[REDACTED]

[REDACTED]

[REDACTED]

[REDACTED]

Appendix 5 Detailed Description of the

[REDACTED]

[REDACTED]

[REDACTED]

[REDACTED]

[REDACTED]	[REDACTED]
[REDACTED]	[REDACTED]
[REDACTED]	[REDACTED]
[REDACTED]	[REDACTED]
[REDACTED]	[REDACTED]
[REDACTED]	[REDACTED]

[REDACTED]

[REDACTED]

[REDACTED]

[REDACTED]

[REDACTED]

[Redacted text block]

[Redacted text block]

[Redacted text block]

- [Redacted list item]

- [Redacted list item]

[Redacted text block]

[REDACTED]

[REDACTED]

[REDACTED]

[REDACTED]

[REDACTED]

[REDACTED]

[REDACTED]

[REDACTED]

[REDACTED]

[REDACTED]

[REDACTED]

[REDACTED]

[REDACTED]

[REDACTED]

[REDACTED]

[REDACTED]

[REDACTED]

[REDACTED]

[REDACTED]

[REDACTED]

[REDACTED]

[REDACTED]

[REDACTED]

[REDACTED]

[REDACTED]

[REDACTED]

[REDACTED]

[REDACTED]

[REDACTED]

[figure not shown]
[REDACTED]

[figure not shown]
[REDACTED]

[REDACTED]

[REDACTED]

Appendix 6 Surgical Reporting Schematics

Appendix 7 Investigator Questionnaire

1. LIST OF ABBREVIATIONS

Abbreviation or Specialist Term	Explanation
AE	Adverse event
ANC	Absolute neutrophil count
CSE	Clinically Significant Event
CTCAE	Common Terminology Criteria for Adverse Events
eCRF	Electronic Case Report Form
FAS	Full Analysis Set
FDA	Food and Drug Administration
GCP	Good Clinical Practice
GMP	Good Manufacturing Practice
ICH	International Conference on Harmonisation
IRB	Institutional Review Board
OTL	On Target Laboratories, Inc.
PP	Per Protocol
SAE	Serious adverse event
SAP	Statistical Analysis Plan
SAS	Safety Analysis Set
TEAEs	Treatment-emergent adverse events

2. INTRODUCTION

The purpose of this plan is to prospectively (*a priori*) outline the types of analyses and presentations of the safety and efficacy data that will form the basis for conclusions regarding this clinical investigation. The analysis defined in this plan should answer the study objectives outlined in the protocol and explain in detail how the data will be handled or analyzed.

This document contains information to support the generation of the efficacy and safety section for the Clinical Study Report (CSR) for Clinical Protocol OTL38-005. This plan contains the detailed descriptions of the statistical methodologies to be applied, as well as the analysis summaries to present the analysis results. Consistently, OTL38 will be referred to as the *study drug*.

2.1. Responsibilities

██████████ will perform the statistical analyses for all clinical data collected. ██████████ is responsible for production and quality control of all datasets, tables, figures, and listings.

2.2. Timing of Analyses

There will be one final analysis for this study after the database lock.

3. STUDY OBJECTIVES AND ENDPOINTS

3.1. Study Objectives

The primary objectives of this study are as follows:

- To estimate the Sensitivity and False Positive rate of OTL38 for malignancy detection during Near Infrared Imaging (NIR).
- To assess the safety and tolerability of single intravenous doses of OTL38.

There are 2 secondary objectives defined for this study.

- To assess the safety of the Fluorescence Imaging Systems for intraoperative imaging when used with OTL38.
- To estimate the efficacy of OTL38 and NIR with respect to the identification of Clinically Significant Events (CSEs).

There are 2 exploratory objectives defined for this study.

- [REDACTED]

3.2. Endpoints

Primary

Sensitivity or True Positive Rate (TPR) [REDACTED]

False positive rate (FPR) [REDACTED]

Secondary

The secondary efficacy endpoint is proportion of patients with at least one CSE as a result of utilizing OTL-38 and Near Infrared Imaging. [REDACTED]

Exploratory

1. [REDACTED]

Safety

1. Incidence rates of all treatment-emergent AEs (TEAEs), adverse device effects (ADEs), and SAEs, from the time of OTL38 administration through follow-up Visit 4.
2. Laboratory parameters (chemistry and hematology) and vital signs collected at: screening, during day of surgery and 7-day follow-up
3. Electrocardiograms (ECG) and physical examinations will be collected at screening, day of infusion, and within 24 hours prior to discharge.

4. STUDY OVERVIEW

4.1. Study Design

This is a phase 2, multi-center, single dose, open-label, exploratory study in patients with folate receptor positive lung nodules scheduled to undergo endoscopic or thoracic surgery per CT/PET imaging based on standard of care. [REDACTED]

[REDACTED]

- | [REDACTED]
- | [REDACTED]

[REDACTED]	[REDACTED]
[REDACTED]	[REDACTED]

- | [REDACTED]
- | [REDACTED]

[REDACTED]

[REDACTED]

[REDACTED]

[REDACTED]

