1 PROTOCOL SYNOPSIS

Study Title	A Phase 2, Single dose, Open-Label, Exploratory Study to Investigate the Safety and Efficacy of OTL38 Injection for Intraoperative Imaging of Folate Receptor Positive Lung Nodules
Protocol Number	OTL-2016-OTL38-005
Sponsor	On Target Labs, Inc. [REDACTED]
Investigational Product	OTL38 Injection: folate analog ligand conjugated with an indole cyanine-like green dye as a solution in vials containing 1.6 mL at 2 mg/mL
Primary Objectives	
 • To estimate the Sensitivity and False Positive rate of OTL38 for malignancy detection during Near Infrared Imaging (NIR). • To assess the safety and tolerability of single intravenous doses of OTL38.
Secondary Objectives	
 • To assess the safety of the Fluorescence Imaging Systems for intraoperative imaging when used with OTL38. • To estimate the efficacy of OTL38 and NIR with respect to the identification of Clinically Significant Events (CSEs).
Exploratory	
 • [REDACTED]
Study Design	
 • This is a phase 2, multi-center, single dose, open-label, exploratory study in suspected lung cancer patients scheduled to undergo endoscopic or thoracic surgery per CT/PET imaging based on standard of care. • [REDACTED]
Treatment	
 • OTL38 is a folate analog ligand conjugated with an indole cyanine-like green dye. • Each patient will be administered a single dose of OTL38 and study-related procedures will last from approximately 2-3 hours before dosing to 24 hours after dosing. • The imaging systems used in this study are not approved for use with OTL38, and are therefore considered investigational for the purposes of this study (see Section 5.8.5 for additional information) Full specifications for [REDACTED]. • The imaging system used by the investigational site will be recorded in the eCRF.

Study Duration	
 • Patients will complete a single dose of OTL38 [REDACTED] initiation of intraoperative imaging. • Safety assessments: during infusion of OTL38; post-surgery; Day 7 (\pm 4), and Day 28 (\pm 7) after surgery. • Estimated total length of study: 18 months • Patient accrual estimate: 12 months

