Eligibility Criteria	
Inclusion:
 
 1. Male and Female patients 18 years of age and older 2. Confirmed diagnosis of adenocarcinoma lung cancer 
OR,
 
 3. Have a primary diagnosis, or at high clinical suspicion, of lung nodule(s) warranting surgery based on CT and/or PET imaging 4. Who are scheduled to undergo endoscopic or thoracic surgery 5. A negative serum pregnancy test at Screening followed by a negative urine pregnancy test on the day of surgery or day of admission for female patients of childbearing potential 6. Female patients of childbearing potential or less than 2 years postmenopausal agree to use an acceptable form of contraception from the time of signing informed consent until 30 days after study completion 7. Ability to understand the requirements of the study, provide written informed consent and authorization of use and disclosure of protected health information, and agree to abide by the study restrictions and to return for the required assessments 
Exclusion:
 
 1. Previous exposure to OTL38 2. Known FR-negative lung nodules 3. Any medical condition that in the opinion of the investigators could potentially jeopardize the safety of the patient 4. History of anaphylactic reactions 5. History of allergy to any of the components of OTL38, including folic acid 6. Pregnancy, or positive pregnancy test 7. Clinically significant abnormalities on electrocardiogram (ECG) at screening. 8. Presence of any psychological, familial, sociological or geographical condition potentially hampering compliance with the study protocol and follow-up schedule 9. Impaired renal function defined as eGFR < 50 mL/min/1.73m² 10. Impaired liver function defined as values > 3x the upper limit of normal (ULN) for alanine aminotransferase (ALT) or aspartate aminotransferase (AST), alkaline phosphatase (ALP), or total bilirubin. 11. Received an investigational agent in another investigational drug or vaccine trial within 30 days prior to surgery 12. Known sensitivity to fluorescent light
Number of Subjects	Up to 110 patients with suspected lung cancer will be enrolled in this study

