4 STUDY OBJECTIVES

4.1 Primary

- To estimate the Sensitivity and False Positive rate of OTL38 for malignancy detection during Near Infrared Imaging (NIR).
- To assess the safety and tolerability of single intravenous doses of OTL38

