5.2 Eligibility Criteria

5.2.1 Inclusion Criteria

To be considered eligible to participate in this study, a patient must meet all the inclusion criteria listed below:

1. Male and Female patients 18 years of age and older
2. Confirmed diagnosis of adenocarcinoma of the lung,
OR,
3. Have a primary diagnosis/high clinical suspicion of lung nodule(s) warranting surgery based on CT and/or PET imaging.
4. Scheduled to undergo endoscopic or thoracic surgery
5. A negative serum pregnancy test at Screening followed by a negative urine pregnancy test on the day of surgery or day of admission for female patients of childbearing potential
6. Female patients of childbearing potential or less than 2 years postmenopausal agree to use an acceptable form of contraception from the time of signing informed consent until 30 days after study completion
7. Ability to understand the requirements of the study, provide written informed consent and authorization of use and disclosure of protected health information, and agree to abide by the study restrictions and to return for the required assessments

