5.2.2 Exclusion Criteria

Patients will be excluded if they meet any of the exclusion criteria listed below:

1. Previous exposure to OTL38
2. Known FR-negative lung nodules.
3. Any medical condition that in the opinion of the investigators could potentially jeopardize the safety of the patient
4. History of anaphylactic reactions
5. History of allergy to any of the components of OTL38, including folic acid
6. Pregnancy, or positive pregnancy test
7. Clinically significant abnormalities on electrocardiogram (ECG) at screening.
8. Presence of any psychological, familial, sociological or geographical condition potentially hampering compliance with the study protocol and follow-up schedule
9. Impaired renal function defined as $eGFR < 50 \text{ mL/min/1.73m}^2$

10. Impaired liver function defined as values $> 3x$ the upper limit of normal (ULN) for alanine aminotransferase (ALT) or aspartate aminotransferase (AST), alkaline phosphatase (ALP), or total bilirubin.
11. Received an investigational agent in another investigational drug or vaccine trial within 30 days prior to surgery.
12. Known sensitivity to fluorescent light

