5.8.1.1 Visit 1 (Screening, up to Day -28)

Prior to the initiation of study-specific screening assessments the Investigator or designee must provide the patient(s) a complete explanation of the purpose and evaluations (procedures and assessments) of the study. Subsequently, the patient must sign and receive a copy of an Informed Consent Form and authorization of use and disclosure of protected health information (PHI) that was approved by the institutional review board (IRB). Once informed consent has been obtained, the eligibility of the patient will be determined, and Screening Period assessments will be performed.

- Signed informed consent
- Complete medical history
- Physical examination
- Height and weight
- Concomitant medication assessment
- Vital signs (temperature, blood pressure, and pulse rate)
- Serum Pregnancy test (for women of childbearing potential)
- 12-lead ECG
- Clinical laboratory assessments including hematology, chemistries, and urine analysis

5.8.1.2 Visit 2- Day of Surgery (Day 1):

- Updated medical history and physical exam
- Concomitant medications assessment
- Clinical laboratory and vital sign assessments will be performed.
- Urine pregnancy test (for women of childbearing potential)
- 12- Lead ECG will be collected at least 15 minutes prior to infusion, and at least 15 minutes prior to surgery after infusion of OTL38 is completed
- A single dose of OTL38 will be infused IV over 60 minutes and will be completed at least one hour prior to initiation of intraoperative imaging and the time will be recorded
- AEs will be recorded during infusion of OTL38
- During and post-surgery any AEs and ADEs will be recorded.

- [REDACTED]

Day 1 – Surgery

This is a phase 2, multi-center, single dose, open-label, exploratory study in suspected lung cancer patients scheduled to undergo endoscopic or thoracic surgery per CT/PET imaging based on standard of care.

[REDACTED]

- [REDACTED]

- [REDACTED]

[Redacted]

[Redacted]	[Redacted]	[Redacted]
[Redacted]	[Redacted]	[Redacted]
[Redacted]	[Redacted]	[Redacted]
[Redacted]	[Redacted]	[Redacted]

[Redacted]

[Redacted]

[Redacted]

[Redacted]

[Redacted]

[Redacted]

[Redacted]

[Redacted]

[Redacted]

[Redacted]

[Redacted]

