8.2 Statistical Methods

This is a phase 2, single dose, open-label exploratory study to estimate the safety and efficacy of OTL38 for intraoperative imaging of folate receptor positive lung nodules in patients diagnosed with FR+ adenocarcinoma of the lung, or with high clinical suspicion of lung nodule(s) warranting surgery based on CT and/or PET imaging. The primary objective of the study is to assess the safety of OTL38 in combination with fluorescent light imaging and to estimate the sensitivity and false positive rate.

Further analytic details for efficacy and safety will be provided in the statistical analysis plan (SAP).

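### Does the folate-receptor-positive label in Protocol 5.1 and SAP 4.1 misstate the population behind the primary estimates?

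*SAP*

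**What the plan says.** Two descriptions of the population stand side by side.

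- **FR-positive wording.** SAP 4.1 describes an "exploratory study in patients with folate receptor positive lung nodules scheduled to undergo endoscopic or thoracic surgery"; Protocol 5.1 uses the same words. Protocol 8.2 is mixed: "in patients diagnosed with FR+ adenocarcinoma of the lung, or with high clinical suspicion of lung nodule(s". There FR+ is attached to the adenocarcinoma branch only.
- **Suspected-cancer wording.** The synopsis describes an "exploratory study in suspected lung cancer patients scheduled to undergo endoscopic or thoracic surgery per CT/PET imaging", and the Day 1 – Surgery text of Protocol 5.8.1.2 repeats this. The synopsis also states: "Up to 110 patients with suspected lung cancer will be enrolled in this study".

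The entry rules are in Protocol 5.2. Inclusion 2 reads "Confirmed diagnosis of adenocarcinoma of the lung" and has no FR condition. Its alternative, inclusion 3, asks for lung nodules warranting surgery on CT and/or PET, again with no FR condition. The only FR criterion is exclusion 2: "Known FR-negative lung nodules". The readable screening list in Protocol 5.8.1.1 contains no FR test.

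The primary efficacy objective, in Protocol 4.1 and SAP 3.1, is "To estimate the Sensitivity and False Positive rate of OTL38 for malignancy detection during Near Infrared Imaging (NIR". SAP 8.1 speaks of identifying lung cancer. Neither mentions FR status in its readable text. The full analysis set, the per-protocol set and the definitions of the two rates are redacted.

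**The concern.** The study estimates two rates and tests no hypothesis, so what those rates mean depends on whom they describe. OTL38 binds the folate receptor, and Protocol 3.2 puts FR positivity at about 85% of lung and pleural malignancies. On that figure some enrolled cancers should be FR-negative and might fluoresce less often, which would put sensitivity in all malignancies below sensitivity in FR-positive ones. The false positive rate could differ too, since Protocol 3.2 reports FR-expressing macrophages in benign nodules that fluoresce.

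SAP 2 says the plan supports the efficacy section of the clinical study report. In the SAP's readable text, 4.1 is the only description of who is enrolled. A report author who copied it could attach an FR-positive label to results from patients who were never selected for FR positivity.

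**Working it through.** **Step 1: compare the label with the rules that decide entry.**

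| Place | Population | FR condition |
|---|---|---|
| Protocol 5.1, SAP 4.1 | patients with FR-positive nodules | yes |
| Protocol 8.2 | adenocarcinoma, or suspected nodules | first branch only |
| Synopsis, Protocol 5.8.1.2 | suspected lung cancer | none |
| Inclusion 2 or 3 | adenocarcinoma, or nodules warranting surgery | none |
| Exclusion 2 | – | removes known FR-negative only |
| Protocol 4.1, SAP 3.1, SAP 8.1 | target is malignancy or lung cancer | none readable |

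A patient of unknown FR status can enter. Protocol 5.1 and SAP 4.1 are therefore narrower than the readable criteria. In Protocol 8.2 the mismatch is a single adjective against inclusion 2.

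**Step 2: ask what the label controls.** Enrolment follows 5.2. The readable SAP bases the primary analysis on the full analysis set (SAP 8). The descriptive sentence in 4.1 feeds into neither.

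**Step 3: illustrate the scale of a misreading.** The plan states no figure on this point, so there is none to reproduce. From the documents: FR-positive share 0.85 (Protocol 3.2) and up to 110 patients (synopsis). Assumed: sensitivity s+ = 95% in FR-positive disease, a range for s− in FR-negative disease, and 77 malignancies (70% of 110, one each).

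- All-malignancy sensitivity p = 0.85·s+ + 0.15·s−
- Gap = s+ − p = 0.15·(s+ − s−)
- 95% half-width = 1.96·√(p(1−p)/77)

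| s− | p | Gap (points) | Half-width (points) |
|---|---|---|---|
| 0% | 80.75% | 14.25 | 8.8 |
| 25% | 84.5% | 10.5 | 8.1 |
| 50% | 88.25% | 6.75 | 7.2 |
| 75% | 92.0% | 3.0 | 6.1 |
| 95% | 95.0% | 0 | 4.9 |

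The largest possible gap is 0.15 × (1 − 0) = 15 points. With s+ = 95%, the gap equals the half-width at s− of about 46%: 0.15 × (0.95 − 0.46) = 7.35 points, and with p = 0.876 the half-width is also about 7.35. With 55 or 99 malignancies (50% or 90% of 110) the crossing point moves to about 33% or 54%.

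Exclusion 2 shrinks the ceiling. If a fraction q of FR-negative cases is removed as known (assumed), the FR-positive share is 0.85/(0.85 + 0.15(1 − q)). That is 0.876 at q = 0.2 and 0.919 at q = 0.5, so the largest gap falls to 12.4 or 8.1 points.

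No gap can be computed for the false positive rate, because the FR-positive share of benign nodules is not given.

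**Step 4: ask whether a table by FR status would help.** With 77 malignancies, 0.15 × 77 ≈ 12 would be FR-negative. At 50% detection the half-width is 1.96·√(0.25/12) ≈ 28 points. Such a row would be too imprecise to settle the matter, and the readable text does not show that FR results will exist for these lesions.

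**The case for a change.** The strongest argument for acting is that two incompatible population statements should not stand in one plan, and that aligning them costs a few words. An estimation study is judged by what its estimate refers to, and under unfavourable assumptions the two readings differ by more than sampling error. The inconsistency is real, and one consistent description would be tidier.

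The argument for a consequence is weaker. Misreporting would require an author to take one sentence from SAP 4.1 and pass over SAP 3.1 and 8.1, as well as the eligibility criteria that a report sets out in any case. It cannot be assumed that FR status will be mostly unknown at reporting: Protocol 8.2.5.3.6 plans listings of immunohistochemistry, although the readable text does not name the markers. The 85% refers to lung and pleural malignancies in general, not to the enrolled mix. Protocol 3.4.1 lists nonspecific localization as a possible concern, so FR-negative lesions may fluoresce and the gap may be small.

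The redactions also limit both sides. The analysis-set and rate definitions, and most of the subgroup list, are hidden. They may carry an FR condition or a breakdown by FR status. A sentence declaring that the primary rates cover all malignancies could contradict text that cannot be seen.

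**Conclusion.** The wording conflict is genuine but clerical. The FR-positive wording of Protocol 5.1 and SAP 4.1 also appears in the study title, where it names the imaging target; as a population description it is looser than the criteria. Analysts and report authors can resolve it sensibly from the entry rules and the stated objective.

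The effect on patients enrolled, data analysed and rates calculated is nil. The 0 to 15 point range is the possible distance between two descriptions of sensitivity, not a bias in the planned estimate. It rests on the protocol's 85% and on assumed detection rates. A breakdown by FR status would rest on about 12 FR-negative lesions (assumed) and on data not shown to exist.

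This conclusion relies on the readable text. Whether the primary rates are restricted by FR status cannot be confirmed while the definitions are redacted. No change to the plan is called for.
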